Appendix 4 Eye Dryness Score Visual Analog Scale

Representation of the EDS VAS. Subjects will grade their symptoms on a scale of 0 (no symptoms) to 100 (severe symptoms) by placing a vertical mark on the horizontal line. Study staff will measure and record the VAS score.

Instructions: Please review your eye dryness. Rate how your eyes feel at this **moment** by drawing a single vertical mark through the horizontal line that represents how your eyes feel.

Appendix 5 Ocular Discomfort Score Visual Analog Scale

Representation of the ODS VAS. Subjects will grade their symptoms at this moment on a scale of 0 (no symptoms) to 100 (severe symptoms) by placing a vertical mark on the horizontal line. Study staff will measure and record the VAS score.

PLEASE COMPLETE THE FOLLOWING QUESTIONS REGARDING YOUR DRY EYE SYMPTOMS.

No Symptoms	Severe Symptoms
Burning/Stinging	_____
Sandy/gritty feeling	_____
Itching	_____
Sensitivity to light	_____
Pain	_____

Appendix 6 Symptom Assessment in Dry Eye Questionnaire

Subjects will grade their symptoms **over the past week** on a scale of 0 to 100 by placing a vertical mark on the horizontal line. Study staff will measure and record the VAS score.

SAnDE QUESTIONNAIRE

PLEASE COMPLETE THE FOLLOWING QUESTIONS REGARDING THE FREQUENCY AND SEVERITY OF YOUR DRY EYE SYMPTOMS.

Frequency of symptoms:

Place a vertical mark on the line to indicate how often, on average, your eyes feel **dry and/or irritated**:

Rarely All the time

Severity of symptoms:

Place a vertical mark on the line to indicate how severe, on average, you feel your symptoms of **dryness and/or irritation**:

Very Mild Very Severe

[figure not shown]
Appendix 7 Unanesthetized Schirmer's Test

Initiate unanesthetized Schirmer's Test in each eye at least 15 minutes after CFS at all visits.

At Visits 1, 2, and 6 initiate additional unanesthetized Schirmer's test OU at least 20 ± 5 minutes after Investigational Product dose).

Unanesthetized Schirmer's test instructions:

- While still inside the plastic sheath, fold the rounded end of the Schirmer's test strip at the first line on the strip (closest to the rounded end).
- Remove the right eye strip from the sheath.
- Ask the subject to look up and gently draw the right lower lid of the unanesthetized eye in a downward and temporal direction.
- Place the rounded end of the strip toward the temporal one-third of the lower eyelid.
- Repeat this procedure in the left unanesthetized eye.
- Darken the room.
- Instruct the subject to focus on the 20/400 E letter on the eye chart.
- Start the timer.
- Remove strips after 5 minutes.
- After removing the strips, place each strip on a flat surface beside a ruler.
- Visualize the leading edge and the lowest point of moisture and, using the ruler, measure a point halfway between the 2 points. Record this value as the amount of wetting.
- Retain Schirmer's test strips in source documentation for confirmatory measurement purposes.

Appendix 8 Fluorescein Solution Administration Using Strips

Use Sponsor-supplied unpreserved sterile saline (if not available, unpreserved sterile water may be used) to moisten the dye on the fluorescein-impregnated strip supplied by the Sponsor.

Remove any excess fluid by shaking fluid from the strip to ensure a consistent amount of dye is dispensed at each assessment.

Instill the dye onto the inferior cul-de-sac of the first eye by touching the strip to the palpebral conjunctiva. Wait approximately 1 minute. Repeat the procedure for the second eye using the same strip. Ask the subject to blink several times to spread the dye.

For corneal fluorescein staining, assess the staining approximately 2 to 2½ minutes after the dye instillation.

The 1-minute waiting period between dye instillation into each eye will allow the evaluator to complete the assessment of the first eye before the 2- to 2½-minute waiting period has elapsed after dye instillation in the second eye.

Use a slit lamp with cobalt blue illumination (465–490 nm) and a Wratten #12 yellow filter to improve the ability to grade fluorescein staining. Grade the 5 areas of the cornea according to the scale for each zone ([Appendix 9](#)).

[figure not shown]
Appendix 9 Corneal Fluorescein Staining Grading

This scale is modified from the corneal grading scale presented in the Tear Film & Ocular Surface Society Dry Eye Workshop II report ([Wolffsohn 2017](#)).

Expanded NEI/Industry Workshop model ([Lemp 1995](#)):

- Cornea is divided into five (5) zones: inferior, nasal, central, temporal, superior; the central zone diameter should be 1/3 the cornea diameter with the 4 equally sized outer zones.

Example of right eye region, expanded NEI/Industry Workshop Model

- Score each zone using a scale of 0 to 4 based upon the PREDOMINANT finding within the zone. Note: The presence of an isolated small area of coalescent staining should be graded according to the predominant appearance in the entire zone.
 - 0= no staining
 - 1= few/rare punctate lesions
 - 2= discrete and countable lesions
 - 3= lesions too numerous to count, but not coalescent
 - 4= coalescent
- Total maximum score equals 20

Appendix 10 Anesthetized Schirmer's Test

Perform anesthetized Schirmer's Test after unanesthetized Schirmer's Test at Visit 2.

Perform anesthetized Schirmer's Test after the final IP ASHRAE 7-point comfort VAS (Visits 2 and 6).

Anesthetized Schirmer's test instructions:

- Instill proparacaine 0.5% drops bilaterally.
- Blot excess from ocular cul-de-sac and periorbital area; wait 5 minutes.
- While still inside the plastic sheath, fold the rounded end of the Schirmer's test strip at the first line on the strip (closest to the rounded end).
- Remove the right eye strip from the sheath.
- Ask the subject to look up and gently draw the right lower lid of the anesthetized eye in a downward and temporal direction.
- Place the rounded end of the strip toward the temporal one-third of the lower eyelid.
- Repeat this procedure in the left anesthetized eye.
- Darken the room.
- Instruct the subject to focus on the 20/400 E letter on the eye chart.
- Start the timer.
- Remove strips after 5 minutes.
- After removing the strips, place each strip on a flat surface beside a ruler.
- Visualize the leading edge and the lowest point of moisture and, using the ruler, measure a point halfway between the 2 points. Record this value as the amount of wetting.
- Retain Schirmer's test strips in source documentation for confirmatory measurement purposes.

Appendix 11

Sponsor Approval Signature

[figure not shown]
[figure not shown]
Study Title: Phase 1/2a, Proof-of-Concept, Multicenter, Parallel, Vehicle-Controlled, Double-Masked, Randomized Study Evaluating the Safety, Tolerability, and Efficacy of IVW-1001 Ophthalmic Eyelid Wipe in Subjects With Dry Eye Disease

Study Number: IVW-1001-CS-101

Version: 1.1

Final Date: 17 April 2024

This clinical study protocol has been approved by the Sponsor.

Appendix 12

Investigator's Signature

Study Title: Phase 1/2a, Proof-of-Concept, Multicenter, Parallel, Vehicle-Controlled, Double-Masked, Randomized Study Evaluating the Safety, Tolerability, and Efficacy of IVW-1001 Ophthalmic Eyelid Wipe in Subjects With Dry Eye Disease

Study Number: IVW-1001-CS-101

Version: 1.1

Final Date: 10 April 2024

By signing below, the Investigator agrees to adhere to the protocol as outlined and agrees that any changes to the protocol must be approved by IVIEW Therapeutics, Inc. prior to seeking approval from the Institutional Review Board.

1. INTRODUCTION

This statistical analysis plan (SAP) for study IVW-1001-CS-101 describes the endpoints, datasets, and analyses planned for the safety and efficacy data of this study. The variables and methods described in this plan supersede those described in the protocol. If revisions are needed after finalizing, then this document will be amended. All SAP amendments will be finalized prior to locking the database and unmasking of the treatment codes to the sponsor. All deviations from the analyses described in the final SAP will be noted in the clinical study report.

In 2017, the Tear Film and Ocular Surface Society Dry Eye Workshop II (TFOS-DEWS II) defined dry eye disease (DED) as “...a multifactorial disease of the ocular surface characterized by a loss of homeostasis of the tear film, and accompanied by ocular symptoms, in which tear film instability and hyperosmolarity, ocular surface inflammation and damage, and neurosensory abnormalities play etiological roles” (Craig 2017). TFOS-DEWS II goes on to state, “The management of DED is complicated, due to its multifactorial etiology...The ultimate aim of DED management is to restore the homeostasis of the ocular surface and tear film, through breaking the vicious cycle of the disease.” A wide range of treatments are available based upon the nature and severity of the patient’s DED. Management of DED generally begins with conventional, low-risk self-administered therapies, including over-the-counter (OTC) lubricant eye drops, and progresses to more advanced therapies as severity increases (Craig 2017). However, many patients are still not optimally treated despite the availability of numerous approved therapeutic products.

As recently reviewed, researchers have discovered that thermal changes at the ocular surface activate cool neurons and may affect surface wetness (Yang 2018). TRPM8 receptors, which are located on the cornea and eyelid at the base of eyelash follicles (Yang 2017), appear to be first activated after evaporation of the tear film (Belmonte 2017); these may be associated with the detection of “dryness” on the eye surface (Parra 2014; Quallo 2015). TRPM8 may also be a direct stimulator of tear secretion from the lacrimal gland (Parra 2010).

To test this hypothesis, a TRPM8 agonist was synthesized (IVW-1001; cryosim-3; C3; 1-diisopropyl-phosphinoyl-nona; Yang 2017). In nonclinical models of mouse DED, single topical ocular doses of C3 0.2% showed activity (Yang 2017). IVW-1001 0.2% singly applied ocular topical doses increased tear secretion in healthy rabbits.

In clinical C3 studies conducted in Korea in subjects with DED, 60 subjects (n=30 per group) participated in a single-dose study, and 40 subjects (n=20 per group) completed a 2-week, repeat-dose study. Cryosim-3 or vehicle (water) was applied with a cotton gauze pad to upper eyelids of subjects with DED (n=30). Cooling sensation, tear film break-up time (TBUT), basal tear secretion, and corneal staining were evaluated. Cryosim-3 was then applied 4 times daily (QID) for 2 weeks to subjects using a pre-loaded single-unit applicator containing C3 2 mg/mL (0.2%) in water (n=20) or water only. After 2 weeks of QID dosing with C3 0.2% as an eyelid wipe, subjects experienced improved signs and symptoms relative to the control (water) group (Yang 2017). An open-label, non-comparative pilot study was also conducted in Korea in 20 subjects with neuropathic ocular pain (Yoon 2021). After 1 month of treatment with C3 0.2% eyelid wipes, subjects experienced improvement in ocular pain symptoms, quality of life, and Schirmer’s test scores.

In this Phase 1/2a study, IVW-1001 Ophthalmic Eyelid Wipes are being evaluated for the treatment of subjects with DED. The final drug product is a single-use, preservative-free, sterile eyelid wipe that is saturated with either C3 0.1% ophthalmic solution, C3 0.2% ophthalmic solution, or a vehicle ophthalmic solution on a polyester cloth. Two wipes (1 for each eye) are sealed into a glass vial. Tweezers are also provided to extract the wipe from the vial. IVW-1001 is a new drug substance, and there is no previous human experience in the United States (US).

2. STUDY DESCRIPTION

2.1. Objectives, Endpoints, and Estimands

Objectives and Endpoints

Objectives	Measures
Primary Safety To assess the safety of IVW-1001 Ophthalmic Eyelid Wipes in subjects with DED	
• Mean change from baseline in:
○ Best-corrected visual acuity (BCVA)○ Slit lamp biomicroscopy○ Intraocular pressure (IOP)○ Dilated ophthalmoscopy• Visual analog scale (VAS) of investigational product (IP) tolerability• Adverse Events (AEs)
Primary Efficacy To assess the efficacy of IVW-1001 Ophthalmic Eyelid Wipes in subjects with DED	
• Mean change from baseline at Day 29 (Week 4/EOS) in the study eye in the unanesthetized Schirmer's test
Exploratory Efficacy To further assess the efficacy of IVW-1001 Ophthalmic Eyelid Wipes with respect to other exploratory efficacy endpoints	
• Mean change from baseline in the study eye at each visit assessed in:
○ Unanesthetized Schirmer's test (Weeks 1, 2, and 3)○ VAS of IP comfort (ASHRAE 7-point scale)○ VAS of Eye Dryness Score (EDS)○ VAS of Ocular Discomfort Score (ODS)○ Symptom Assessment in Dry Eye (SAnDE) questionnaire○ Corneal fluorescein staining (inferior zone)○ Corneal fluorescein staining (total of all zones)

	
○ Anesthetized Schirmer's test● Proportion of subjects with a ≥ 10 mm increase in unanesthetized Schirmer's test score● Proportion of subjects with a ≥ 10 mm increase in anesthetized Schirmer's test score
--	--

Primary Estimand:

The estimand for the primary efficacy endpoint in this study is:

- The difference between IVW-1001 and Vehicle in the mean change from baseline at Day 29 (Week 4) in the study eye in the unanesthetized Schirmer's test score estimated using all data collected from the mITT population.

2.2. Study Design

Protocol IVW-1001-CS-101 is a Phase 1/2a study designed to evaluate the safety, efficacy and tolerability of IVW-1001 Ophthalmic Eyelid Wipe in subjects with DED. It is a randomized (1:1:1), multicenter, parallel, vehicle-controlled, double-masked study. The study includes treatment-experienced subjects, with a focus on those with a prior suboptimal response to artificial tear therapy. A total of 150 subjects will be randomized to one of the following treatments:

- IVW-1001 Ophthalmic Eyelid Wipe 0.2% (High Dose)
- IVW-1001 Ophthalmic Eyelid Wipe 0.1% (Low Dose)
- IVW-1001 Ophthalmic Eyelid Wipe Placebo (Vehicle)

The study is divided into 2 sections:

1. A 7-day single, subject-masked vehicle run-in period
2. A 28-day, active, double-masked treatment period, commencing on Day 1, the date of treatment assignment and initial treatment administration

Subjects will self-administer the treatment twice daily to the upper eyelid of both eyes for the 28-day section of the study, excluding the mornings of Visits 3, 4, 5 and 6 (Days 8, 15, 22 and 29) when the dose will be self-administered with study staff oversight. Subjects will not be eligible for rescue treatment during the study.

2.3. Schedule of Activities and Visit Windows

The structure and exam schedule of each phase of the study is outlined below in Table 1.

Visit windows indicated are intended to provide structure for the study. Any data collected during out-of-window visits will not be excluded, but will be evaluated as a part of the analysis, when appropriate, and will be included in the subject data listings.

Table 1. Schedule of Activities

Procedures	Study Period Visit Visit Timing (Window)	Screening [a]	Baseline/ Randomization [b]	Week 1 [b]	Week 2 [b]	Week 3 [b]	Week 4/ EOS/ET [b]
		1 Day -7 to 1 (+2)	2 Day 1	3 Day 8 (±1)	4 Day 15 (±2)	5 Day 22 (±2)	6 Day 29 (-3 to +1)
Informed consent		X					
Eligibility determination (inclusion/exclusion criteria)		X	X				
Demographics		X					
Medical/Ophthalmic history		X	X				
Concomitant medications		X	X	X	X	X	X
Urine pregnancy test (WOCBP only [c])		X	X				
EDS VAS		X	X	X	X	X	X
ODS VAS		X	X	X	X	X	X
IP ASHRAE 7-point comfort VAS [d]		X	X	X	X	X	X
BCVA (and refraction [e]) OU		X	X	X	X	X	X
Slit lamp biomicroscopy OU		X	X	X	X	X	X
Corneal fluorescein staining OU		X	X	X	X	X	X
Unanesthetized Schirmer's test OU [f, g]		X [f, g]	X [f, g]	X [f]	X [f]	X [f]	X [f, g]
Anesthetized Schirmer's test OU [h, i]			X [h, i]				X [i]
IOP OU		X	X				X [j]
Randomization/assignment		X[k]	X				
In-office IP administration OU [l]		X	X [l]	X [l]	X [l]	X [l]	X [l]
SAnDE questionnaire [m]		X	X	X	X	X	X
IP tolerability VAS [m]		X	X	X	X	X	X
Fundoscopy (dilated ophthalmoscopy) OU		X					X
Dispense/Return IP with accountability/compliance		X	X	X	X	X	X
AE assessment		X	X	X	X	X	X

AE, adverse event; BCVA, best-corrected visual acuity; EDS, Eye Dryness Score; EOS, End of Study; ET, Early Termination; IOP, intraocular pressure; IP, investigational product; ODS, Ocular Discomfort Score; OU, both eyes; SAnDE, Symptom Assessment in Dry Eye; VAS, visual analog scale; WOCBP, women of childbearing potential.

- [a] The Screening Visit can occur any time of the day.
- [b] The Baseline, Week 1, Week 2, Week 3, and EOS Visits should be conducted between 7:00 am and 12:00 pm.
- [c] All WOCBP must have a negative pregnancy test result at Screening Visit 1 and Baseline Visit 2 prior to randomization in the study.
- [d] IP ASHRAE 7-point comfort VAS to be performed pre-dose and 5 ± 2 , 15 ± 2 , 30 ± 5 , and 60 ± 5 minutes post-dose, unless the score at 5 and 15 minutes is 0, in which case the 30- and 60-minute assessments can be omitted.
- [e] Refraction at Visit 1 only unless ≥ 3 line reduction in VA.
- [f] Unanesthetized Schirmer's to be performed at least 15 minutes post-CFS.
- [g] Unanesthetized Schirmer's to be performed 20 ± 5 minutes post-IP administration.
- [h] Anesthetized Schirmer's to be performed after unanesthetized Schirmer's.
- [i] Anesthetized Schirmer's to be performed post final IP ASHRAE 7-point comfort VAS.
- [j] IOP to be performed post anesthetized Schirmer's.
- [k] Assignment of run-in IP (vehicle).
- [l] IP administration must be performed at least 20 minutes after completion of CFS. Subjects should not dose IP at home the morning of Visits 2, 3, 4, 5, or 6.
- [m] SAnDE questionnaire and IP tolerability VAS to be performed between 5 and 15 minutes post-dose.

2.3.1. Study Day Definition

In addition to visit date, study day will be calculated for each visit date as a continuous representation of visit timing. The study day of an event is defined as the relative day of the event, starting with the date of the first study drug administration (reference date) as Day 1 (there will be no Day 0).

The study day of events occurring before the first study drug administration will be calculated as:

$$\text{Study Day} = (\text{Date of Event} - \text{Date of First Study Drug Administration})$$

For events occurring on or after Day 1, study day will be calculated as:

$$\text{Study Day} = (\text{Date of Event} - \text{Date of First Study Drug Administration}) + 1$$

Note: Study days will only be calculated for events with complete dates and will be undefined for events that are 'Ongoing' at the end of the study.

2.4. Study Treatments, Randomization and Masking

Central randomization using an Interactive Web Response System (IWRS) will be utilized to provide assignment of a specific anonymized code, corresponding to the IP to which the subject is randomized at the baseline visit.

A total of 150 subjects will be randomized to one of the following treatments:

- IVW-1001 Ophthalmic Eyelid Wipe 0.2% (High Dose)
- IVW-1001 Ophthalmic Eyelid Wipe 0.1% (Low Dose)
- IVW-1001 Ophthalmic Eyelid Wipe Placebo (Vehicle)

Study treatment randomization codes and procedures for breaking codes will be maintained by the central randomization provider.

Specific procedures used for masking include anonymized codes and barcoding of IP without identifiable names, marking, or labels. In rare cases, masking can be broken for an individual subject in the event of an unexpected serious adverse event (SAE) necessitating identification of the specific IP received.

2.4.1. Emergency Unmasking

Only in case of medical emergency or occurrence of SAEs will the code be unmasked via the central randomization service. The code may then be made available to the Investigator, the Sponsor, and/or other personnel involved in the monitoring or conduct of this study, as appropriate.

2.5. Study Eye Selection

While both eyes (OU) will be dosed with the IP, a study eye (SE) will be designated by the Data Management team at the baseline visit, following the process below:

- If both eyes have an unanesthetized Schirmer's score between 5-10 mm inclusive, the SE will be the eye with the lower score.

- If both eyes have the same unanesthetized Schirmer's score, the SE will be the eye with the highest qualifying total corneal fluorescein staining (CFS) score.
- If both eyes have the same total CFS score, the right eye (OD) will be designated as the SE.

3. HYPOTHESIS, SAMPLE SIZE AND POWER

3.1. Statistical Hypothesis

The primary efficacy endpoint is the mean change from baseline (CFB) at Day 29 (Week 4/EOS) in the SE in the unanesthetized Schirmer's test.

The clinical hypothesis is that IVW-1001 Ophthalmic Eyelid Wipe administered BID bilaterally for 29 days is more effective than Vehicle when evaluating tear production in subjects with DED.

The following 2-sided hypothesis will be tested:

$$H_0: \Delta = 0$$

$$H_a: \Delta \neq 0$$

Where Δ is the difference in mean CFB in the unanesthetized Schirmer's score as measured at Day 29 (Week 4) between the IVW-1001 Ophthalmic Eyelid Wipe and Vehicle treated groups.

In brief, the null hypothesis indicates that the mean CFB in the unanesthetized Schirmer's score as measured at Day 29 for subjects treated with IVW-1001 Ophthalmic Eyelid Wipe 0.2% or IVW-1001 Ophthalmic Eyelid Wipe 0.1% will not differ from the mean CFB in the unanesthetized Schirmer's score for subjects treated with Vehicle. The alternative hypothesis indicates that there is a significant difference at Day 29 between subjects treated with IVW-1001 Ophthalmic Eyelid Wipe and subjects treated with Vehicle.

3.2. Sample Size and Power

Approximately 150 subjects will be enrolled (50/group) to obtain approximately 138 subjects who complete the study (46/group). For the primary efficacy endpoint, this sample size of 46 subjects per group should provide at least 80% power to detect a difference between the vehicle group and each of the IVW-1001 groups of 3.0 mm or greater in the unanesthetized Schirmer's test, assuming a standard deviation (SD) of 5.0 mm and a 0.05 two-sided significance level.

3.3. Multiplicity Adjustment

Due to the early phase of the study and because the primary objective is the assessment of safety, there will be no adjustments for multiplicity in the testing of the efficacy endpoints.

4. ANALYSIS POPULATIONS

Three analysis populations will be defined for this study: Safety (SAF), modified Intent-to-Treat (mITT) and Per-Protocol (PP). The determination of which subjects will be included in each population will be determined prior to the final database lock and unmasking of treatment codes. The analysis populations in this study will be defined as follows:

4.1. Safety (SAF)

All subjects who receive at least one (1) dose of the IP will be included in the SAF population. This is the population that will be used for all safety and AE analyses. Subjects will be analyzed in the treatment arm according to the IP they received, regardless of the group they were randomized to, and no subjects (or data) will be excluded due to protocol deviations that occur during the study.

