6 ALLOCATION AND DOSING OF INVESTIGATIONAL PRODUCT

6.1 Allocation to Treatment Groups

After the vehicle run-in period, during which all subjects receive vehicle, qualified subjects will be randomized 1:1:1 to 1 of 3 treatment groups to receive one of the following: IVW-1001 Ophthalmic Eyelid Wipe 0.1%, IVW-1001 Ophthalmic Eyelid Wipe 0.2%, or vehicle.

6.1.1 *Subject Assignment*

All subjects will receive the same vehicle control run-in at the Screening Visit (single-masked), and at the Baseline Visit, subjects will receive and be dispensed IP according to the treatment group to which they are assigned.

6.1.2 *Study Eye Selection*

The study eye will be designated by Data Management at randomization at the Baseline Visit. If both eyes have an unanesthetized Schirmer's test score between 5 and 10 mm inclusive, the study eye will be the one with the lower score. If both eyes have the same an unanesthetized Schirmer's test score, the study eye will be the one with the highest qualifying total CFS score. However, if both eyes have the same total qualifying CFS score, the right eye will be designated as the study eye. Site personnel are not required to designate the study eye.

Note that dosing of study medication will be in both eyes (OU).

6.1.3 *Randomization Procedures*

Central randomization using the IWRS will be utilized to provide assignment of a specific anonymized code, corresponding to vehicle during the run-in period at the Screening Visit and separately to the IP to which the subject is randomized (IVW-1001 Ophthalmic Eyelid Wipe 0.1%, IVW-1001 Ophthalmic Eyelid Wipe 0.2%, or vehicle) at the Baseline Visit.

Trial treatment randomization codes and procedures for breaking codes will be maintained by the central randomization provider.

6.1.4 *Masking*

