9.3 Analysis Populations

The safety and tolerability endpoints will be analyzed using the Safety Set, and the primary and secondary efficacy endpoints will be analyzed using the mITT and Per Protocol (PP) Sets. The Safety and mITT Sets will include all randomized subjects who receive at least 1 dose of the IP. The PP Set will include all randomized subjects who meet all of the enrollment criteria and complete the efficacy evaluations at Day 29 without any significant protocol deviations that could impact the integrity of the data. As a sensitivity analysis, the primary and secondary efficacy endpoints will be analyzed using the PP Set.

For the Safety Set, subjects will be analyzed in the group according to the treatment received during the majority of the study, irrespective of the group to which they were randomized, and no subjects will be excluded from this study population because of protocol deviations. For the mITT Set, subjects will be analyzed in the group to which they were randomized, irrespective of what they actually received, and no subjects will be excluded from this study population because of protocol deviations. The analysis sets will be determined prior to unmasking the treatment assignments.

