4.2. Modified Intent-to-Treat (mITT)

All randomized subjects who receive at least one (1) dose of the IP will be included in the mITT population. The mITT will be the population used for the efficacy analyses. Subjects will be analyzed according to the treatment arm assigned at randomization, irrespective of compliance or any deviations in the study drug received. In addition, no subjects (or data) will be excluded due to protocol deviations that occur during the study.

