7.7. Changes to Protocol-Planned Analyses

Changes to the protocol-planned analyses include the following:

- The protocol indicates that as a sensitivity analysis, the primary and secondary efficacy endpoints will be analyzed using the PP population. The secondary endpoints were meant to be defined as 'exploratory' as no efficacy endpoints are defined in the protocol as secondary. Since the primary objective of the study is safety and all the exploratory endpoints will be analyzed at all visits using the mITT population, only the primary endpoint will be analyzed using the PP population.
- The protocol indicates that for the efficacy endpoints, missing data will be imputed using last observation carried forward. Since the amount of missing efficacy data throughout the study is very small, no imputation for missing data will be performed.
- The protocol indicates that for the efficacy endpoints, appropriate methods will be used to control the Type I error rate for multiple comparisons of the 2 dose groups versus the control. Since this is an early phase study where the primary objective is safety, and because there are many endpoints being tested at all visits (primary and exploratory), no multiplicity adjustments will be performed.

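### SAP 4.1 drops the randomized-only condition and the majority-treatment rule for the safety population, so its literal wording admits subjects who were dosed only in the vehicle run-in

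*SAP*

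**What the plan says.** SAP 4.1 sets membership with "All subjects who receive at least one (1) dose of the IP will be included in the SAF population" and the arm with "Subjects will be analyzed in the treatment arm according to the IP they received, regardless of the group they were randomized to". SAP 7.2 repeats the membership condition, again without requiring randomization.

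Protocol 9.3 differs on both counts. For membership it says "The Safety and mITT Sets will include all randomized subjects who receive at least 1 dose of the IP". For the arm, "subjects will be analyzed in the group according to the treatment received during the majority of the study".

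The next SAP section, 4.2, keeps the condition for the efficacy set: "All randomized subjects who receive at least one (1) dose of the IP will be included in the mITT population".

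On precedence, SAP 1 says "The variables and methods described in this plan supersede those described in the protocol". SAP 7.7 opens with "Changes to the protocol-planned analyses include the following" and gives three items: the per-protocol analysis, imputation and multiplicity. The safety population is not among them.

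The design feature that matters is in Protocol 6.1: "After the vehicle run-in period, during which all subjects receive vehicle, qualified subjects will be randomized 1:1:1".

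**The concern.** In a parallel trial without a run-in, a safety set of everyone who took at least one dose, grouped by what they took, would raise no question. Here every subject takes vehicle before randomization, and vehicle is one of the three named IPs. A rule that mentions neither randomization nor a period therefore reaches people and doses outside the randomized comparison.

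Two things follow from the literal text. A subject dosed at Visit 1 who fails eligibility at Visit 2 meets the membership condition, and the only IP that subject received is vehicle. A subject randomized to an active arm has received two IPs, and SAP 4.1 does not say which one counts.

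The SAP calls safety the primary objective and uses this population for all safety and adverse event analyses. Because the SAP claims precedence, an analyst who finds the protocol's narrower definition has no clear authority to use it.

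**Working it through.** **1. The definitions side by side.**

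| | Protocol 9.3, Safety | SAP 4.1 and 7.2, Safety | SAP 4.2, mITT |
|---|---|---|---|
| Must be randomized | yes | not stated | yes |
| At least one dose of IP | yes | yes | yes |
| Arm | treatment received for most of the study | IP received (4.1) | arm assigned |

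The SAP uses the word *randomized* where it wants that limit (4.2, and the population lines of 6.2 and 6.3). Its absence from 4.1 therefore reads as a different rule.

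**2. Is run-in vehicle an IP?** Protocol 5.1 names vehicle as an IP. Protocol 7.5.1 lists an in-office IP (vehicle) dose at Screening. Protocol 8.5 places the first IP dose in the run-in. SAP Table 1 footnote k speaks of run-in IP. Footnote l tells subjects not to dose IP at home on the morning of Visit 2, when they can only hold run-in vehicle. Usage is not uniform: Protocol 5.3.3 dispenses vehicle for the run-in and IP at randomization, and SAP 2.4 ties IP to the randomized assignment. Nothing in SAP 4.1 selects the narrower sense.

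**3. Who is dosed but never randomized?** SAP 6.1 counts screen failures at Visit 2, after the run-in. Their number is not given. If a fraction f of run-in subjects fails at Visit 2 and 150 are randomized, the number added is n = 150 × f / (1 − f). For **assumed** f of 10%, 20%, 30% and 40%:

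- n = 16.7, 37.5, 64.3 and 100, or about 17, 38, 64 and 100.
- Literal safety population, 150 + n: 167, 188, 214 and 250.
- As a percentage of the 150 randomized: 111%, 125%, 143% and 167%.
- Literal Vehicle arm, 50 + n: 67, 88, 114 and 150.

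These figures show only how membership depends on f. If all 150 are dosed, any f above zero gives a percentage above 100, which bears on intent in step 5.

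**4. The arm of active subjects.** With 150 randomized 1:1:1, 150 × 2/3 = 100 are planned for active treatment. A completer has 7 days of vehicle and 28 of active. Under the protocol's majority rule the active share is 28 / (7 + 28) = 28/35 = 80%, so the arm is unique. SAP 4.1 has no corresponding rule.

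Restoring the protocol's words would not be a complete repair. If the run-in counts as part of the study, a subject who stops active treatment before 7 days has had more days on vehicle than on active.

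**5. What the SAP appears to intend.** SAP 2.2 makes Day 1 the date of treatment assignment and first treatment. SAP 2.3.1 makes Day 1 the date of first study drug administration. SAP 2.4 describes the IP as the one assigned at the baseline visit. SAP 4.1 itself refers to the group a subject was randomized to. SAP 6.1 expresses every population as a percentage of those randomized. Together these point to a randomized-only set starting on Day 1. With that set, the planned safety population is 150, in arms of 50, 50 and 50 if all are dosed as assigned.

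**The case against.** The strongest reply is that nobody would program the literal rule. The arms are the three randomized treatments, the arm sentence in SAP 4.1 is ordinary as-treated wording that presupposes randomization, and SAP 6.1 would print percentages above 100. SAP 4 also requires membership to be settled before lock and unmasking, which gives a checkpoint. SAP 7.7 says that changes *include* its three items, so it does not claim to be complete. And since SAP 4.1 is silent on subjects who received two IPs, the protocol's majority rule may still fill that gap.

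Much of this stands. A reader might infer that 100 active-arm subjects cannot be placed in any arm. The documents do not support that: SAP 2.2, 2.3.1 and 2.4 point to the Day 1 treatment, and what is missing is an explicit sentence. A reader might also infer from SAP 7.2.2 that exposure and compliance would run from the first run-in wipe. That section concerns study drug exposure and days on treatment, SAP 2.2 places treatment in the 28-day section, and SAP 2.3.1 starts study drug on Day 1. The anchor is clear enough, and a clarifying phrase would suffice.

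The reply does not dispose of membership. There SAP 4.1 is not silent: it states a condition wider than the protocol's, SAP 7.2 repeats it, and the SAP claims precedence. Intent has to be inferred from other sections, because no SAP sentence limits the safety population to randomized subjects.

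**Conclusion.** The membership rule in SAP 4.1 is wrong as written, and its arm rule is incomplete. The weight is minor to should-fix. Confidence is high that the wording differs from Protocol 9.3 and that the literal rule admits Visit 2 screen failures. The cause is most likely a drafting error, and nothing shows that the analysis will be run on the literal rule.

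The conclusion rests on run-in vehicle being an IP, which both documents say in several places though not uniformly, and on some dosed subjects failing at Visit 2, which SAP 6.1 foresees.

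A reader might go further and infer that the Vehicle adverse event rate will be diluted by a definite amount, making active treatment look worse. The documents do not support that. They give neither a run-in failure rate nor adverse event rates, so any such figure would rest wholly on assumptions.

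**What to change.** Replace the definition in SAP 4.1, and match it in SAP 7.2, with wording such as: *All randomized subjects who take one or more doses of double-masked IP on or after Day 1, analyzed under the IP received for most of the double-masked treatment period, whatever arm was assigned.* Tying the arm to the double-masked period also removes the early-stopper ambiguity that the protocol's wording leaves.

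For consistency, state in SAP 7.2.2 that the first wipe and the first dose of IP both mean the first double-masked dose on Day 1. List run-in adverse events of subjects who were never randomized separately from the arms. Record in SAP 7.7 that the arm rule now refers to the double-masked period.

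The cost is a few sentences in a SAP amendment, which SAP 1 allows before database lock and unmasking. No change to data collection or to the planned sample size is needed.
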